**CONFIDENTIAL**

207660

The participant is re-treated at Week 20 visit in Blind Phase and completes the Week 4 visit in Open-label Phase.

The participant completes the Week 24 visit in Blind Phase.

2. All required database cleaning activities have been completed and interim database release and database freeze has been declared by Data Management.
3. All criteria for unblinding the randomization codes have been met.
4. Randomization codes have been distributed according to RandAll NG procedures.
5. Interim analyses will be performed.

The interim analyses will be performed for regulatory submission. However subject level data will not be disclosed to people who work at the sites including investigators.

All planned interim analyses (i.e. Study population, Efficacy and Safety analyses) will be performed using data up to Week 24 visit for all participants.

For Rehabilitations, the data at Screening visit and Week 12 visit will be used for the interim analysis.

For Adverse Events, Liver Events and Medication, the data up to Week 24 visit is defined by using the start date. If the start date of these data is earlier than or same as the date of Week 24 visit defined above, these data will be included in the data up to Week 24 visit. Otherwise the data will not. See the decision tree ([Appendix 14](#)) to determine the Week 24 visit and date of the participant.

Cardiovascular Events will not be output in the interim analysis.

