Safety2	
 
This population consists of all participants in Safety1 population, who receive study treatment at least twice.
 
The participants will be analyzed based on the treatment actually given.
 
	
 
Safety
 

Safety3	
 
This population consists of all participants who are randomized in the study and who receive study treatment at least three times
 
The participants will be analyzed based on the
 
	
 
Safety
 

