Physical examination (simplified version)		X 				X		X 1,t				X		X
Medical history	X	X 												
Vital signs m	X	X 				X		X 1,t				X		X
Height	X													
Body weight	X					X u	X u					X u	X u	
Pulmonary function test	X	X				X	X u					X	X u	X
Electrocardiogram	X					X u	X u					X u	X u	
Pregnancy test n	X	X 				X u	X u					X s, u	X u	X
Laboratory test o	X					X						X		X
Adverse events p	X	X	X	X	X	X	X	X	X	X	X	X	X	X
Concomitant medications/therapies	X	X 	X	X	X	X	X	X	X	X	X	X	X	X
Testing for neutralising antibodies q	X					X								X

- Test items for screening must be performed from 4 weeks to 1 weeks before Day 1 visit (±3 days).
- Eligibility evaluation (Qualification for Retreatment Visit: QRV) will be performed at V5 as a starting point if a participant does not meet the criteria only. The evaluation is performed at a 4-week interval, V5 as a starting point, The QRV when a participant meets the criteria will be a same day as the injection in the next treatment period.
- If a participant is evaluated to meet the eligibility for the injection in the blind phase at V5, the participant will move forward to Part 2 in the open-label phase (Namely, V5 in Part 1 and V1 in Part 2 is a same day). If the participant does not meet the eligibility, QRV will be performed 4 weeks later, at V5 as a starting point.
- If a participant is evaluated to meet the eligibility at V5 in the open-label phase, the participant will move forward to the next treatment phase (V5 and V1 in the next treatment phase is a same day). If the participant does not meet the eligibility, QRV is performed 4 weeks later, V5 as a starting point. If V5 in each treatment phase is at Week 48 after initial injection, V5 will be considered to be completion visit (FV). However, for the testing items, pre-scheduled tests at

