**10.12.7. Safety Tables****10.12.7.1. Interim Analyses**

Safety: Tables					
No.	Population	IDSL / Example Shell	Title	Programming Notes	Deliverable
Adverse Events (AEs)					
3.01.	Safety 1	AE1	Summary of All Adverse Events until Week 24 visit by System Organ Class and Preferred Term	ICH E3 Treatment Emergent Three treatment arms (240, 400 and 240 + 400U)	IA SAC
3.02.	Safety 1	AE1	Summary of All Adverse Events until Week 24 visit by System Organ Class and Preferred Term in Blind Phase	Blind Phase (until second dose) See the Section 10.4.2. Two treatment arm (240 and 400U)	IA SAC
3.03.	Safety 1	AE1	Summary of All Adverse Events within 84 days from the initial dose by System Organ Class and Preferred Term in Blind Phase	Blind Phase (within 84 days) See the Section 10.4.2. Two treatment arm (240 and 400U)	IA SAC
3.04.	Safety 2	AE1	Summary of All Adverse Events until Week 24 visit by System Organ Class and Preferred Term in Open Label Phase (2nd Treatment)	Open Label Phase (2nd Treatment) See the Section 10.4.2. Three treatment arms (240, 400 and 240 + 400U)	IA SAC
3.05.	Safety 1	AE5A	Summary of All Adverse Events until Week 24 visit by Maximum Intensity by System Organ Class and Preferred Term	ICH E3 Treatment Emergent Use AE1 or AE1CP if Grade/Intensity not used; otherwise use AE5A/B (with a Total column across all grades/severities, which provides same detail as AE1)	IA SAC

CONFIDENTIAL

207660

Safety: Tables					
No.	Population	IDSL / Example Shell	Title	Programming Notes	Deliverable
3.06.	Safety 1	AE5A	Summary of All Adverse Events until Week 24 visit by Maximum Intensity by System Organ Class and Preferred Term in Blind Phase	Blind Phase (until second dose) See the Section 10.4.2 . Two treatment arm (240 and 400U)	IA SAC
3.07.	Safety 1	AE5A	Summary of All Adverse Events within 84 days from the initial dose by Maximum Intensity by System Organ Class and Preferred Term in Blind Phase	Blind Phase (within 84 days) See the Section 10.4.2 . Two treatment arm (240 and 400U)	IA SAC
3.08.	Safety 2	AE5A	Summary of All Adverse Events until Week 24 visit by Maximum Intensity by System Organ Class and Preferred Term in Open Label Phase (2nd Treatment)	Open Label Phase (2nd Treatment) See the Section 10.4.2 . Three treatment arms (240, 400 and 240 + 400U)	IA SAC

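### Interim 2nd-treatment adverse-event percentages pool 12-week and 4-week follow-up, so they understate a 12-week risk if anyone is re-treated late

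*SAP*

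**What the plan says.** References are to the amended plan within the SAP document.

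- **Purpose and cut (section 3.1).** "The interim analyses will be performed for regulatory submission". All interim analyses "will be performed using data up to Week 24 visit for all participants". An AE is kept under this condition: "If the start date of these data is earlier than or same as the date of Week 24 visit defined above".
- **Where the cut falls (section 3.1).** For re-treatment at Week 12 or Week 16 it is the open-label Week 12 visit. The third path reads: "The participant is re-treated at Week 20 visit in Blind Phase and completes the Week 4 visit in Open-label Phase". The fourth reads: "The participant completes the Week 24 visit in Blind Phase". Section 3.1 refers to the decision tree in Appendix 14 for each participant's visit and date.
- **Timing of the next injection (section 10.2.1, footnotes b and v).** "The QRV when a participant meets the criteria will be a same day as the injection in the next treatment period". If that is not possible, it may follow within a window of up to 4 days.
- **Denominator (section 4).** Safety 2 is defined thus: "This population consists of all participants in Safety1 population, who receive study treatment at least twice". It sets no follow-up condition. The efficacy counterpart, ITT2, does require an assessment after the second treatment.
- **Tables (section 10.12.7.1).** Tables 3.04, 3.08, 3.14, 3.18, 3.22, 3.27, 3.31, 3.35 and 3.40 cover the 2nd treatment and use Safety 2. Section 8.1 makes the statistic the number and percentage of participants with at least one event.

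**The concern.** A crude percentage can be read as a risk only if everyone in the denominator was observed for about the same time. Here a participant with 28 days after the second injection counts the same as one with 84 days, and events after the cut are scored as no event. The shortfall comes from the administrative cut, not from the length of the treatment cycle.

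The same interim package reports the first cycle in a fixed 84-day window (for example Table 3.03; flag defined in section 10.4.2). Someone who sets first-injection and second-injection percentages side by side would see the repeat 400-unit injection favoured by the cut alone. The table of AEs of special interest (3.27), which includes possible distant spread of toxin, has the same property. The reader cannot correct for it, because the exposure displays (section 8.6; Tables 3.58 to 3.60) cover number of injections and dosage, not follow-up time.

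**Working it through.** **Step 1: follow-up after the second injection at the cut.** Cut-off week = re-treatment week + open-label visit week named in section 3.1.

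| Re-treated at | Cut-off visit | Cut-off week | Days observed |
|---|---|---|---|
| Week 12 | Open-label Week 12 | 12 + 12 = 24 | 84 |
| Week 16 | Open-label Week 12 | 16 + 12 = 28 | 84 |
| Week 20 | Open-label Week 4 | 20 + 4 = 24 | 28 |
| Week 24 | Blind-phase Week 24 | 24 | about 0, if injected that day and counted |

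The Week 20 row reproduces the plan's own 4-week figure. The last row is an inference from the Week 24 cut and same-day injection.

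**Step 2: formula.** Let R be the true 12-week AE risk after the second injection, R4 the risk by Week 4, and w the shares of Safety 2 by re-treatment week. Then

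reported % = (w12 + w16) × R + w20 × R4 + w24 × 0.

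The SAP gives neither R nor the shares, so both are **assumed**. Take R = 30%. R4 is set in three ways:

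- constant hazard: R4 = 1 − 0.70^(1/3) = 11.2%
- 70% of the risk by Week 4: R4 = 21%
- all of it by Week 4: R4 = 30%

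**Step 3: results** (reported %, relative error in brackets).

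| Shares at Weeks 12/16/20/24 | Constant hazard | 70% by Week 4 | 100% by Week 4 |
|---|---|---|---|
| 80/10/7/3% | 27.8 (−7.4%) | 28.5 (−5.1%) | 29.1 (−3.0%) |
| 60/20/12/8% | 25.3 (−15.5%) | 26.5 (−11.6%) | 27.6 (−8.0%) |
| 40/25/20/15% | 21.7 (−27.5%) | 23.7 (−21.0%) | 25.5 (−15.0%) |
| 85/15/0/0% | 30.0 (0) | 30.0 (0) | 30.0 (0) |

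Worked example, row 2, constant hazard: 0.80 × 0.30 + 0.12 × 0.112 = 0.253. With R = 10% or 50% the relative errors are similar (worst cases −28.1% and −26.7%).

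**Step 4: without the Week 24 group.** Suppose same-day Week 24 injections do not enter Safety 2 at the interim.

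- 70% at Weeks 12–16 and 30% at Week 20: 0.70 × 0.30 + 0.30 × 0.112 = 24.4% (−18.8%) under constant hazard. If 60% of the risk falls by Week 4 (R4 = 18%), it is 26.4% (−12%).
- 85% and 15%: 0.85 × 0.30 + 0.15 × 0.112 = 27.2% (−9.4%) and 28.2% (−6%).

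The Week 20 path is therefore enough to produce the effect. If all AEs fell by Week 4 and nobody from Week 24 were counted, the error would be zero.

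**The case against.** **The truncation is declared and temporary.** All nine titles say the data run to the Week 24 visit. No 12-week risk is defined as a target for the second cycle, and the final analysis repeats these tables without the cut (for example Table 3.64). The only treatment comparison the plan specifies is 400 against 240 units, not first against second cycle. This stands as mitigation. But the titles do not tell the reader that individual follow-up differs threefold, and the final tables come after the submission package.

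**The 0-day group may not exist.** A reader might infer that participants injected at Week 24 certainly sit in the denominator with no follow-up. The documents do not settle this. The decision tree in Appendix 14 is not in the text available here. The second injection belongs to an open-label visit that may fall up to 4 days later, and it is unclear whether such an injection counts as a second treatment at the cut. The objection stands for this group only; the 4-week path is explicit.

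**The effect may be small.** With shares of 90/5/5% at Weeks 12–16/20/24 and constant hazard, the table shows 27.6% instead of 30%. That is 2.4 points, or about 3 people if all 120 randomized were in Safety 2. For a rare event the expected shortfall could be under one participant. This stands too.

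**Column distortion.** A reader might infer that the initial 400-unit column is diluted more than the 240-unit column. That would need later re-qualification in the 400-unit group, for which the SAP gives no evidence.

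**Conclusion.** The point holds in a limited form. The nine interim tables mix 84-day and 28-day follow-up in one crude percentage, possibly with some participants who have almost none. The percentages are correct as counts to a declared cut. As a 12-week or full-cycle risk, or beside the 84-day first-cycle tables, they are too low if two things occur together: someone in the denominator was re-treated at Week 20 or later, and some first AEs of the cycle start after that person's cut.

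The direction follows from the text; the size does not. The range of about 3% to 28% relative rests wholly on assumed re-treatment shares and AE timing, and both ends include a Week 24 group with no follow-up. Without that group, the scenarios tried give 6% to 19%. The plan therefore does not show that the submitted repeat-dose risk will be materially understated; it leaves the reader unable to tell. This is a reporting weakness that is cheap to repair, not a flaw in the efficacy conclusions or the final safety analysis.

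**What to change.** In section 10.12.7.1, keep all of Safety 2 and the crude counts. Add to the nine tables, or at least to the all-AE, drug-related, serious-AE and special-interest tables:

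- person-time from the second injection to the cut-off date, by treatment column; and
- an exposure-adjusted incidence rate, or a Kaplan-Meier 84-day cumulative incidence censored at the cut-off. The rate is fully comparable only if the hazard is roughly constant. The Kaplan-Meier figure does not need that and can be set directly beside the first-cycle 84-day percentage.

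In section 3.1, state that a second injection given on or after the participant's cut-off visit date does not place that participant in Safety 2 for the interim, and check that Appendix 14 agrees. AEs starting on that date stay in the overall table and the listing.

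Restricting the denominator to participants re-treated at Week 12 or 16 is less attractive. It removes injected participants and their observed AEs from the second-cycle tables according to when they re-qualified, which is itself a post-treatment outcome.

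The cost is SAP wording and a little extra programming, with no new data. The repeat-dose figures may look somewhat less favourable.

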### **3.2. Final Analyses**

The final planned primary analyses will be performed after the completion of the following sequential steps:

1. All participants have completed the study as defined in the protocol.
2. All required database cleaning activities have been completed and final database release and database freeze has been declared by Data Management.
3. Final analyses will be performed.

CONFIDENTIAL

207660

**4. ANALYSIS POPULATIONS**

Population	Definition / Criteria	Analyses Evaluated
Screened	
 
Comprise of all screened participants
 
	
 
Study Population
 

Enrolled	
 
Comprise of all participants who meet the eligibility criteria at a screening and Day 1 visit.
 
	
 
Study Population
 

Intent-To-Treat 1 (ITT1)	
 
This population consists of all participants who are randomized in the study and who have at least 1 post-baseline efficacy assessment:
 
ITT is the primary efficacy analysis population, and the participants will be analyzed in line with the randomized treatment group
 
Any participant who receives a study treatment randomization number will be considered to have been randomized.
 
	
 
Study Population
 
Efficacy
 

ITT2	
 
This population consists of all participants in ITT1 population, who have at least 2 study treatments and who have at least 1 efficacy assessment after the 2nd treatment.
 
	
 
Study Population
 
Efficacy
 

ITT3	
 
This population consists of all participants in ITT2 population, who have at least 3 study treatments and who have at least 1 efficacy assessment after the 3rd treatment.
 
	
 
Study Population
 
Efficacy
 

ITT4	
 
This population consists of all participants in ITT3 population, who have 4 study treatments and who have at least 1 efficacy assessment after the 4th treatment.
 
	
 
Study Population
 
Efficacy
 

Safety1	
 
This population consists of all participants who are randomized in the study and who receive study treatment at least once
 
The participants will be analyzed based on the treatment actually given.
 
	
 
Safety
 

Safety2	
 
This population consists of all participants in Safety1 population, who receive study treatment at least twice.
 
The participants will be analyzed based on the treatment actually given.
 
	
 
Safety
 

Safety3	
 
This population consists of all participants who are randomized in the study and who receive study treatment at least three times
 
The participants will be analyzed based on the
 
	
 
Safety
 

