**7.1.3. Population of Interest**

The primary efficacy analyses will be based on the Intent-To-Treat 1 population, unless otherwise specified.

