**7.1.4. Strategy for Intercurrent (Post-Randomization) Events**

Intercurrent event: early withdrawal from study

Strategy : if MAS score is missing because of an early withdrawal from the study, the participant will be regarded as a non-responder.

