**7.1.5.1. Statistical Methodology Specification**

Endpoint / Variables

 
• Responder Rate of MAS in the elbow flexors at Week 6 of the initial dose
 

Model Specification

 
• To summarize the primary endpoint without statistical model 
 
○ The primary endpoint will be calculated as the proportion of participants whose MAS score decreased by at least 1 level from the baseline in the ITT1 population.
 
○ The intergroup difference in the responder rate and its 95% confidence interval (Wald-type) will be computed.
 
 
 

Data Convention

 
• The MAS scores, 0, 1, 1+, 2, 3 and 4 will be encoded to 0, 1, 2, 3, 4 and 5, respectively, for the analyses.
 

Definition of Responder and Responder rate

“Responder” is defined as a participant whose MAS score decrease by at least 1 level from the baseline.
 
Responder Rate will be calculated as below.
 
Responder Rate (%) = (Number of Responders) / (Number of participants in ITT1 population) x 100
 
 
• If MAS score of a given participant is missing at Week 6, then this participant will be regarded as a non-responder.
 

Model Results Presentation

 
• The difference in the responder rate (400 units – 240 units) and its associated 95% CI will be presented.
 

Subgroup Analyses (Rehabilitation)

 
Subgroup analyses will be performed by baseline rehabilitation in the Section 5.4.
 
The difference (400 units – 240 units) and its 95% CI will be presented.
 

Subgroup Analyses (baseline MAS score)

 
Subgroup analyses will be performed by baseline MAS score of the elbow (3 or 4) used as randomization strata.
 
The difference (400 units – 240 units) and its 95% CI will be presented.
 

Supportive Analyses

 
The difference in the responder rate will be estimated using Mantel-Haenszel method to consider a stratification factor, that is baseline MAS score of the elbow (3 or 4).
 
Mantel-Haenszel rate difference (400 units – 240 units) and its 95% CI will be calculated.
 

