**10.12.4. Study Population Tables****10.12.4.1. Interim Analyses**

Study Population Tables					
No.	Population	IDSL / Example Shell	Title	Programming Notes	Deliverable
Participant Disposition					
1.01.	ITT1	ES1	Summary of Participant Disposition for the Participant Conclusion Record (Week 24)	ICH E3, FDAAA, EudraCT Participant disposition at Week 24. Include total arm (240 U + 400 U)	IA SAC
1.02.	Screened	ES6	Summary of Screening Status and Reasons for Screen Failure	Journal Requirements	IA SAC
1.03.	Enrolled	NS1	Summary of Number of Participant by Site ID	EudraCT/Clinical Operations	IA SAC
Protocol Deviation					
1.04.	ITT1	DV1	Summary of Important Protocol Deviations	ICH E3 Include total arm (240 U + 400 U)	IA SAC
Population Analysed					
1.05.	Screened	SP1	Summary of Study Populations	IDSL	IA SAC
Demographic and Baseline Characteristics					
1.06.	ITT1	DM1	Summary of Demographic Characteristics	ICH E3, FDAAA, EudraCT Include total arm (240 U + 400 U)	IA SAC
1.07.	Enrolled	DM11	Summary of Age Ranges	EudraCT	IA SAC
1.08.	ITT1	DM5	Summary of Race and Racial Combinations	ICH E3, FDA, FDAAA, EudraCT	IA SAC

CONFIDENTIAL

207660

Study Population Tables					
No.	Population	IDSL / Example Shell	Title	Programming Notes	Deliverable
1.09.	ITT1	POP_T1	Summary of Baseline Efficacy Parameters	
 
MAS scores in finger, thumb, wrist and elbow
 
Randomization Strata
 
Numeric Rating Scale for pain
 
Disability Assessment Scale
 
Include total arm (240 U + 400 U)
 
	IA SAC
Prior and Concomitant Medications					
1.10.	ITT1	CM1	Summary of Prior Medications	Include total arm (240 U + 400 U)	IA SAC
1.11.	ITT1	CM1	Summary of Concomitant Medications	ICH E3 Include total arm (240 U + 400 U)	IA SAC
1.12.	ITT1	POP_T2	Summary of Rehabilitation	Include total arm (240 U + 400 U)	IA SAC
1.13.	ITT1	SAFE_T4	Summary of Actual Dosage in Exposed Muscle Region by Treatment Cycle and Muscle Region.		IA SAC
1.14.	ITT1	SAFE_T4	Summary of Actual Dosage in Exposed Joint by Treatment Cycle and Joint		IA SAC

CONFIDENTIAL

207660

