**10.12.9. ICH Listings****10.12.9.1. Interim Analyses**

ICH: Listings					
No.	Population	IDSL / Example Shell	Title	Programming Notes	Deliverable
Participant Disposition					
1.	Screened	ES7	Listing of Reasons for Screen Failure	Journal Guidelines	IA SAC
2.	ITT1	ES2	Listing of Reasons for Study Withdrawal	ICH E3	IA SAC
3.	Screened	ES9	Listing of Participants Who Were Rescreened		IA SAC
4.	ITT1	BL1	Listing of Participants for Whom the Treatment Blind was Broken	ICH E3	IA SAC
5.	ITT1	TA1	Listing of Planned and Actual Treatments	IDSL	IA SAC
Protocol Deviations					
6.	ITT1	DV2	Listing of Important Protocol Deviations	ICH E3	IA SAC
7.	ITT1	IE3	Listing of Participants with Inclusion/Exclusion Criteria Deviations	ICH E3	IA SAC
Populations Analysed					
8.	Enrolled	SP3	Listing of Participants Excluded from Any Population	ICH E3	IA SAC
Demographic and Baseline Characteristics					
9.	ITT1	DM2	Listing of Demographic Characteristics	ICH E3	IA SAC
10.	ITT1	DM9	Listing of Race	ICH E3	IA SAC
Prior and Concomitant Medications					
11.	ITT1	CM3	Listing of Medications	IDSL	IA SAC
12.	ITT1	POP_L1	Listing of Rehabilitation		IA SAC

CONFIDENTIAL

207660

ICH: Listings					
No.	Population	IDSL / Example Shell	Title	Programming Notes	Deliverable
13.	ITT1	Study Specific	Listing of Other Surgical Procedure		IA SAC
Exposure and Treatment Compliance					
14.	ITT1	POP_L2	Listing of Exposure Data	ICH E3	IA SAC
Efficacy Endpoints					
15.	ITT1	EFF_L1	Listing of Modified Ashworth Scales	
 
• Values
 
• Changes from baseline
 
• Responders
 
	IA SAC
16.	ITT1	EFF_L1	Listing of Disability Assessment Scales	
 
• Values
 
• Changes from baseline
 
• Main Assessment Parameter
 
	IA SAC
17.	ITT1	EFF_L1	Listing of Numeric Rating Scale for pain	
 
• Values in each joint
 
• Changes from baseline in only elbow joint
 
	IA SAC
18.	ITT1	EFF_L1	Listing of Clinical Global Impression of Change	
 
• CGI by an investigator and a patient
 
• Values
 
	IA SAC
19.	ITT1	EFF_L2	Listing of Patient-Reported Benefit of Injection		IA SAC
20.	ITT1	EFF_L3	Listing of Time to Patient Reported Onset of Spasticity Symptom Relief		IA SAC
21.	ITT1	EFF_L3	Listing of Time to Qualification for Retreatment		IA SAC

CONFIDENTIAL

207660

ICH: Listings					

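### ITT1 excludes randomized participants with no post-baseline efficacy assessment, whom the plan's own missing-data rule would count as non-responders, and the disposition displays exclude them too

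*SAP*

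**What the plan says.** The references are to the amended SAP; the plan it amends has the same ITT1 definition and the same ITT1 disposition tables.

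- **Population.** Section 4 defines ITT1: "This population consists of all participants who are randomized in the study and who have at least 1 post-baseline efficacy assessment". It adds: "Any participant who receives a study treatment randomization number will be considered to have been randomized". ITT1 is therefore a subset of those randomized.
- **Use.** Section 7.1.3: "The primary efficacy analyses will be based on the Intent-To-Treat 1 population, unless otherwise specified". In Section 7.1.5.1 the responder rate divides the number of responders by the number of participants in ITT1.
- **Missing data.** Section 7.1.4 gives the strategy for early withdrawal: "if MAS score is missing because of an early withdrawal from the study, the participant will be regarded as a non-responder". Section 7.1.5.1 extends it to any reason: "If MAS score of a given participant is missing at Week 6, then this participant will be regarded as a non-responder". Section 10.7.2 names this non-responder imputation.
- **Disposition.** Section 6.2 promises early withdrawals with their reasons, by treatment group and in total, and that item carries no restriction to ITT1. In Appendix 12 the population column is ITT1 for disposition Tables 1.01 and 1.15, for Listings 2 and 35 ("Listing of Reasons for Study Withdrawal"), for important deviations (Tables 1.04 and 1.16, Listings 6 and 38) and for broken blinds (Listings 4 and 37).

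**The concern.** The non-responder rule can act only on people already in the denominator. A participant who is randomized and then never assessed after baseline is the clearest case of early withdrawal with a missing Week 6 MAS, yet that participant is removed by a condition observed after randomization. The condition does no work for this endpoint: the responder rate needs no post-baseline value, because a missing value already has an assigned outcome.

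Two things are at stake. One is the denominator of the primary responder rates, and so their difference and its interval. The other is whether the disposition, withdrawal-reason, deviation and blind-break displays account for everyone randomized.

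**Working it through.** **Inputs from the SAP.** 120 randomized, 60 per group (Section 2.3); 2 × 60 = 120 agrees. The SAP gives no assumed responder rates and no loss rate, and Section 2.4 plans no formal test. The responder counts and losses below are therefore assumptions.

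**Step 1: who is affected.** Apply Sections 4 and 7.1 to a randomized participant with no Week 6 MAS.

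| Participant | In ITT1? | Primary outcome |
|---|---|---|
| Assessed at Week 2 or 4, then leaves | Yes | Non-responder |
| Leaves before Week 2, MAS recorded at the withdrawal visit | Yes | Non-responder |
| Leaves with no post-baseline efficacy assessment of any kind | No | Excluded |

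The second row follows from the schedule in Section 10.2.1, which marks MAS at the Final Visit column (Week 48 or withdrawal). Only the third row contradicts Section 7.1.4.

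**Step 2: effect on one arm's rate.** With r responders among 60 randomized and k participants excluded (none of whom can be a responder):

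- all randomized: r/60
- ITT1: r/(60 − k)

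Assume r = 42: 42/60 = 70.0%; k = 1 gives 42/59 = 71.2%; k = 3 gives 42/57 = 73.7%. The rate can only rise.

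**Step 3: effect on the difference.** Difference d = p1 − p0, with Wald 95% CI d ± 1.96 × √(p1(1 − p1)/n1 + p0(1 − p0)/n0), as in Section 7.1.5.1. Assume 42/60 on 400 units and 30/60 on 240 units: d = 20.0 points, SE = √(0.0035 + 0.00417) = 0.0876, CI 2.8 to 37.2. In percentage points:

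| k excluded | 400-unit arm only | 240-unit arm only | k from each arm |
|---|---|---|---|
| 1 | 21.2 (4.1 to 38.3) | 19.2 (1.9 to 36.4) | 20.3 (3.1 to 37.6) |
| 3 | 23.7 (6.6 to 40.7) | 17.4 (−0.0 to 34.8) | 21.1 (3.8 to 38.3) |
| 5 | 26.4 (9.4 to 43.3) | 15.5 (−2.1 to 33.0) | 21.8 (4.5 to 39.1) |

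Equal losses only multiply the difference by 60/(60 − k), for example 20.0 × 60/57 = 21.1.

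**Step 4: range over assumed rates.** Let the 400-unit rate run from 40% to 80%, with the 240-unit rate 20 points lower, and lose 1 to 5 participants. Loss from the 400-unit arm only gives differences of 20.7 to 27.3 points. Loss from the 240-unit arm only gives 19.7 down to 14.5. Equal loss gives 20.3 to 21.8.

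**Step 5: displays.** A third-row participant is absent from Tables 1.01, 1.15, 1.04 and 1.16 and from Listings 2, 35, 6, 38, 4 and 37. The participant is still counted in Tables 1.05 and 1.17 (study populations, Screened) and listed in Listings 8 and 39 (exclusions from any population, Enrolled). If injected, the participant is also in Safety1, which needs no post-baseline assessment. Safety1 feeds the displays of adverse events leading to withdrawal (Tables 3.37 to 3.39 and 3.113 to 3.115, Listings 28 and 59).

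**The case against.** The other side has real substance.

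- A reader might infer that everyone who leaves before Week 2 is dropped. The schedule does not support that. MAS is due at the withdrawal visit, and NRS, DAS and CGI are due there for those who withdraw within 12 weeks of the last injection. Only participants never assessed after baseline are lost. This stands and narrows the group considerably.
- A reader might infer that these participants vanish from the report, or that withdrawals caused by treatment are hidden. That is not so: the exclusion outputs and the Safety1 displays still carry them. What is missing is their entry in the disposition, withdrawal-reason, deviation and blind-break displays.
- A reader might infer that the comparison is no longer by randomized arm, or that the bias favours 400 units. Section 4 keeps participants in their randomized group; the set is incomplete, not re-assigned. The difference can move either way.
- The sizes rest on invented counts. Five unassessed losses in one arm and none in the other would be unusual after a single blinded treatment session.
- No hypothesis is tested (Sections 2.4 and 5.5), so no formal decision rests on the interval.
- Section 2.1 reports one change from the protocol's analysis, and it does not concern populations. ITT1 may therefore be protocol-defined.

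None of this explains why a population condition should override the imputation rule for the participants it does affect.

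**Conclusion.** The inconsistency holds in a narrow form. Randomized participants with no post-baseline efficacy assessment are excluded from the primary denominator, although the plan's own rule would make them non-responders. They are also left out of the disposition, withdrawal-reason, deviation and blind-break displays, which falls short of what Section 6.2 promises on early withdrawal.

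Under the assumed 42 of 60, one exclusion adds 1.2 points to that arm's rate (71.2 − 70.0) and three add 3.7 (73.7 − 70.0). The effect on the difference takes its sign from the arm that loses participants and is small when losses are similar. The document does not give the number affected, and it may be zero. The point merits correction because it concerns the primary denominator and the remedy is simple. The likely size does not make it a critical flaw.

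**What to change.** - In Sections 4, 7.1.3 and 7.1.5.1, base the primary responder analysis on all randomized participants, analysed as randomized, with a missing Week 6 MAS counted as non-response. Limiting the set to those randomized and injected would still condition on an event after randomization.
- Keep ITT1 as now defined as a sensitivity set. The secondary elbow, finger and wrist responder rates in Section 7.2.5.1 share its denominator, so state the choice for them as well.
- Run Tables 1.01, 1.15, 1.04 and 1.16 and Listings 2, 35, 6, 38, 4 and 37 on all randomized participants.
- If the protocol defines ITT1, declare the change in Section 2.1.

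No new data are needed. The cost is revised wording, changed population entries in Appendix 12, possibly a declared departure from the protocol, and responder rates that may be slightly less favourable.
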